3.6 Study Timeline

Primary Completion:

The study will reach primary completion 24 months from the time the study opens to accrual.

Study Completion:

The study will reach study completion 36 months from the time the study opens to accrual.

Definition of end of the Study

The arm will be completed when 17 patients have evidence of disease progression by RECIST, unacceptable toxicity, withdrawal of consent, or discontinuation of the trial for any other reason. Patients who have RECIST-defined PD as assessed by the investigator but who, in the opinion of the investigator, have evidence of continued clinical benefit from study drug may continue to receive the study medication. In such cases, these patients must continue to be followed for safety and efficacy assessments as per the schedule of assessments.

At the completion or discontinuation of study medication, all patients will be seen within 30 days for an end of therapy evaluation. This will include a safety assessment for AE's SAE's. Any unused medication will be destroyed

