9. STUDY CALENDAR

Table 9-1 Visit evaluation Schedule		Screening / Baseline	Day 1 of Cycle 1 (28d) +/- 3	Day 1 of Cycle 2 (28d) +/- 3	Day 1 of Subsequent cycles (28d) +/- 3	Day 1 of study treatment (EoT) (at last visit, or up to 30 days from last dose)
Visit Number	1	2	3	4, 5..		Last
Day of cycle	D-30 to -1	D1	D29	D57, D85..		Last
Obtain Informed Consent	X					
Patient history						
Inclusion/exclusion criteria	X					
Diagnosis and extent of cancer	X					
Demography	X					
Relevant medical history/current medical conditions	X					
Prior antineoplastic therapy (meds, surgery, radiation)	X					
Prior/concomitant medications	X	X	X	X	X	X
Surgical and Medical Procedures	X	X	X	X	X	X
Physical examination						
Performance status (WHO)	X	X	X	X	X	X
Height	X					
Weight	X	X	X	X	X	X
Vital signs	X	X	X	X	X	X

Table 9-1. Visit evaluation Schedule (continued)		Screening / Baseline	Day 1 of Cycle 1 (28d) +/- 3	Day 1 of Cycle 2 (28d) +/- 3	Day 1 of Subsequent cycles (28d) +/- 3	End of study treatment (EoT) (at last visit, or up to 30 days from last dose)
Visit Number	1	2		3	4, 5,...	Last
Day of cycle	D-30 to-1	D1		D29	D57, D85..	Last
Lab assessments*	X	X		X	X	X
CBC	X	X and at cycle 1 d14		X and at cycle 2 d14	X	X
Chemistry	X	X and at cycle 1 d14		X and at cycle 2 d14	X	X
Creatinine clearance	X					
Serum Pregnancy test for women of childbearing potential	X (-7 to -1 days)					
Imaging						
Standard of care imaging of neck/neck/abdomen/pelvis (CT, MRI) as indicated to areas of known/ suspected disease	X				X (within 0-7d prior to every odd cycle)	
Standard of Care Imaging of the brain at baseline and then as clinically indicated (MRI/CT)	X				X (if known or suspected brain metastases)	
Safety						
Adverse Events	X	X	X	X	X	X
ECG	X					
Drug administration			Continuous			

*Please refer to Table 9-3 for local Clinical laboratory parameters

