Patients will be evaluated upon discontinuation of the study treatment by a clinic visit. At that time all assessments listed for End Of Treatment will be performed. A note will be entered into the clinical trial record will be completed, giving the date and reason for stopping the study treatment.

At a minimum, all patients who discontinue study treatment, including those who refuse to return for a final visit, will be contacted for safety evaluations during the 30 days following the last dose of treatment.

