9.1.4 Assessment types

9.1.4.1 Efficacy assessments

Efficacy evaluations will be via revised RECIST 1.1 criteria on imaging performed at the conclusion of every 2 cycles. Target lesions will be identified prior to initiation of therapy on imaging and will be followed on subsequent imaging.

Physical exam findings of progressive disease will be considered as sufficient for documented progression if the record records biopsy proven tumor measurements in 2 dimensions and shows an increase in both dimensions of 20%.

Imaging exams will be according to standard of care guidelines to areas of known/suspected disease. These will include CT of the neck, chest, abdomen and pelvis as well as MRI of the brain. Other tests may be clinically indicated, these will be ordered according to disease and patient specific guidelines. Imaging of the brain will be required at baseline by CT or MRI per standard of care for Anaplastic Thyroid Cancer.

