10.1 Primary outcome measure

The primary endpoint will be overall response assessed 8 (+/-4) weeks from start of treatment using RECIST v1.1 criteria (please see details below for how this will be measured and defined).

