The best overall response is the best response recorded from the start of the treatment until disease progression/recurrence (taking as reference for progressive disease the smallest measurements recorded since the treatment started). The subject's best response assignment will depend on the achievement of both measurement and confirmation criteria.

Target Lesions	Non-Target Lesions	New Lesions	Overall Response	Best Response for this
----------------	--------------------	-------------	------------------	------------------------

				Category Also Requires:
CR	CR	No	CR	n/a
CR	Non-CR/Non-PD	No	PR	N/a
PR	Non-PD	No	PR	
SD	Non-PD	No	SD	Documented at least once ≥ 4 wks. from baseline
PD	Any	Yes or No	PD	no prior SD, PR or CR
Any	PD*	Yes or No	PD	
Any	Any	Yes	PD	
In exceptional circumstances, unequivocal progression in non-target lesions may be accepted as disease progression.				
Subjects with a global deterioration of health status requiring discontinuation of treatment without objective evidence of disease progression at that time should be reported as " symptomatic deterioration ". Every effort should be made to document the objective progression even after discontinuation of treatment.				

Note: If subjects respond to treatment and are able to have their disease resected, the patient's response will be assessed prior to the surgery.

Duration of Response

Duration of overall response: The duration of overall response is measured from the time measurement criteria are met for CR or PR (whichever is first recorded) until the first date that recurrent or progressive disease is objectively documented (taking as reference for progressive disease the smallest measurements recorded since the treatment started).

The duration of overall CR is measured from the time measurement criteria are first met for CR until the first date that recurrent disease is objectively documented.

Duration of stable disease: Stable disease is measured from the start of the treatment until the criteria for progression are met, taking as reference the smallest measurements recorded since the treatment started.

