10.1.4 Measurement Time Points

The outcome will be measured as long as the patient remains without progression and getting scans for assessment. Patients will be followed for survival as long as they remain consented.

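### No tumour imaging is scheduled once abemaciclib is permanently stopped, so very early stoppers have no scan in the primary window and all who stop without progression have none for PFS or response duration

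*Combined protocol and SAP*

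**What the plan says.** **Scan timing.** The body-imaging row of Table 9-1 (Section 9) has a baseline entry and one on-study entry, "X (within 0-7d prior to every odd cycle". Section 9.1.4.1 agrees, with "imaging performed at the conclusion of every 2 cycles", and Section 10.1.3 also repeats CT every two cycles.

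**End of treatment.** The last column of Table 9-1 is "End of study treatment (EoT) (at last visit, or up to 30 days from last dose". It is filled for blood counts, chemistry and adverse events, but not for imaging. For that visit Section 9.1.3 says "At that time all assessments listed for End Of Treatment will be performed", and otherwise asks for safety contact over 30 days. Section 3.6 describes the end-of-therapy evaluation in the same spirit: "This will include a safety assessment for AE's SAE's".

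**Interruptions.** Section 9.1 fixes the cycle at 28 days and keeps visits on the count from Cycle 1 Day 1 when treatment is interrupted. It does not address permanent stopping.

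**Measurement after stopping.** Section 10.1.4 says "The outcome will be measured as long as the patient remains without progression and getting scans for assessment", with survival follow-up for as long as consent lasts. Section 10.1.3 adds "Every effort should be made to document the objective progression even after discontinuation of treatment", but in the paragraph on symptomatic deterioration. Neither gives a date or interval.

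**Endpoints.** Section 10.1: "The primary endpoint will be overall response assessed 8 (+/-4) weeks from start of treatment using RECIST v1.1 criteria". Section 12.4.2 computes the response rate in the full analysis set, meaning all consented patients with at least one dose. Section 10.1.2 limits evaluability for response to patients whose disease has been re-evaluated. Section 12.5.2 censors PFS at the latest date known alive or disease-free and does not impute missing data.

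**The concern.** Section 4 foresees patients stopping without progression, through unacceptable toxicity or by decision of the investigator or patient. For them the calendar simply ends. Two things are at stake.

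- **Response.** A patient who stops before the first on-study scan may have responded, but no planned assessment would show it. The decision rules turn on 0 of 9 and 3 of 17, so one lost responder can change the outcome.
- **PFS and duration of response.** Both need progression to be dated. Without scans, the PFS event drifts to the date of death, or the patient is censored at a survival-contact date well after the last image. Either way, time in which the tumour was not examined is credited as progression-free, and this happens for patients who could not stay on the drug.

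The plan is also uneven. Sections 3.6, 9.1.2 and 12.1 require efficacy follow-up for patients treated beyond RECIST progression, who have already had their PFS event. No such requirement covers patients who stop before having one.

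**Working it through.** **1. Where the scans fall.** Day 1 of cycle c is day 28(c - 1) + 1, and the scan is 0-7 days earlier.

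| Cycle | Day 1 | Scan days |
|---|---|---|
| 3 | 28 x 2 + 1 = 57 | 50-57 |
| 5 | 28 x 4 + 1 = 113 | 106-113 |
| 7 | 28 x 6 + 1 = 169 | 162-169 |

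The primary window is 8 - 4 = 4 weeks to 8 + 4 = 12 weeks, or days 28-84. Exactly one scheduled scan, on days 50-57, lies inside it. The 3-day visit window blurs the edges slightly, hence 'about day 50' below.

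**2. Who is affected.**

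| Patient | Scan in primary window? | Later scheduled scans? |
|---|---|---|
| Dose interrupted, then resumed | Yes (Section 9.1 keeps the calendar) | Yes |
| Permanent stop without progression, before about day 50 | No | No |
| Permanent stop without progression, after the cycle 3 scan | Yes, already done | No |

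**3. The plan's design figures.** The inputs from Section 12.6.2 are p0 = 0.05, p1 = 0.30, 9 patients in stage 1 (stop at 0 responses), 8 more in stage 2, and success at 3 or more of 17. The probability of success is

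P(p) = sum over x = 1 to 9 of Bin(x; 9, p) x Pr[Bin(8, p) >= 3 - x].

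P(0.05) = 0.0466 and P(0.30) = 0.9045. The stated 0.05 and 0.9 reproduce.

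**4. Effect on the decision rule (assumed loss rates).** Suppose a fraction q of responses is lost because the patient stopped before the first scan and is counted as a non-responder. The effective rate is p(1 - q), and the chance of 0 of 9 is (1 - p(1 - q))^9.

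| q | Effective p1 | Power | Chance of 0/9 at p1 | Type I error, at 0.05(1 - q) |
|---|---|---|---|---|
| 0 | 0.300 | 0.905 | 0.040 | 0.047 |
| 5% | 0.285 | 0.882 | 0.049 | 0.041 |
| 10% | 0.270 | 0.855 | 0.059 | 0.036 |
| 15% | 0.255 | 0.824 | 0.071 | 0.031 |

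**5. Effect of the denominator.** Section 12.4.2 and Section 10.1.2 treat an unscanned patient differently. As an illustration with 3 responders and 2 unscanned patients, the full analysis set gives 3/17 = 17.6% (exact 95% CI 3.8-43.4%). Dropping the two gives 3/15 = 20.0% (4.3-48.1%).

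**6. Direction and rough size for PFS.** I simulated 400,000 patients with exponential times, scans every 56 days, and 20% assigned to stop for toxicity at a time between 0.5 and 2 months. For assigned stoppers whose progression had not been detected by the stopping date, the PFS event moves to death. Median post-progression survival is 1.5-2 months. All these values are assumptions.

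- True median PFS of 2 months: the reported median is 2.8-2.9 months if scans continue and 3.2-3.5 without off-treatment scans. Restricting the effect to patients truly progression-free at stopping gives 3.0-3.2.
- True median PFS of 3 months: the reported median does not move, because it sits on a scan date. The mean rises.

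**The case against.** The strongest reply is that the gap is narrow and its effect is assumed.

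- **Primary endpoint.** A reader might infer that any patient who stops without progression lacks a scan for response. The documents do not support that. The cycle 3 scan lies inside the primary window, so later stoppers already have it. Section 6 handles most toxicity by interruption and dose reduction, and Section 9.1 keeps those patients on the calendar. This stands: only permanent stops before about day 50 are affected.
- **Off-drug imaging is not forbidden.** Section 9.1.3 lists what must be done, Section 10.1.4 does not tie measurement to being on drug, and the scans are standard of care. Section 9.1.4.1 also accepts progression on physical examination, for a biopsy-proven tumour growing 20% in both dimensions. So it would be wrong to say that progression off treatment can never be seen, and the simulation, which assumes exactly that, overstates the shift. But imaging left to local practice is not a schedule, and the examination route covers only tumours that can be measured clinically.
- **Conservative for response.** Counting unscanned patients as non-responders lowers type I error, as step 4 shows. True, but it costs power, and Section 10.1.2 leaves open whether they are counted at all.
- **PFS is secondary and descriptive.** With 17 patients, the sampling 95% range of the median in the 2-month scenario is about 1.8-4.5 months, wider than the shift. That limits the harm, but a bias in a known direction is worth removing when removal is cheap.

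**Conclusion.** The concern holds in a limited form. No section sets a scan date after permanent discontinuation. For response, this affects only patients who stop without progression before about day 50, and their status is contradictory between Sections 10.1.2 and 12.4.2. For PFS and duration of response, it affects everyone who stops without progression. Together with the censoring rule in Section 12.5.2, it biases PFS upward.

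The direction for PFS follows from the documents; the size does not. The power range of 0.88-0.82 rests on an assumed loss of 5-15% of responses, all scored as non-responses. The PFS shift of a few tenths of a month rests on an assumed 20% stopping early, exponential times and no detection of progression off drug. With a 3-month true median, the median does not move at all. The design's sample size, type I error and power are correct as stated and need no change. This is a worthwhile, inexpensive improvement; it does not invalidate the trial.

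**What to change.** 1. In Table 9-1 and Section 9.1.4.1, state that a patient who stops abemaciclib without documented progression stays on the existing 8-weekly imaging schedule, counted from Cycle 1 Day 1, until progression, new anti-cancer therapy, death or withdrawal of consent. Section 9.1 already uses this count for interruptions, so only the continuation after permanent stopping is new.
2. In Section 10.1, state that the week-8 scan is done, and counts for the primary endpoint, even if the drug has been stopped.
3. In Sections 10.1.2 and 12.4.2, state that full analysis set patients with no post-baseline scan count as non-responders, so that the two sections agree.
4. In Section 12.5.2, censor PFS for patients without an event at the last adequate tumour assessment.

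The cost is one calendar entry and a few sentences. The scans are the standard-of-care scans the patient would have had on drug. A few patients must return for imaging after stopping, and some will be too ill to attend, so the gap will shrink but not close completely.

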9.1 Visit schedule and assessments

Table 9-1 lists the protocol schedule and assessments and indicates when particular assessments will be performed with an “X”. The cycle length is fixed at 28 days, and will be maintained regardless of whether there were dose modifications or interruptions in therapy. If treatment with abemaciclib is interrupted, future visits and assessments will continue as listed from Cycle 1 day as Day#1 for the purpose of scheduling.

Visit windows of \pm 3 days from scheduled study assessments will apply during and beyond Cycle 1.

9.1.1 Screening/Baseline Procedures

Assessments performed exclusively to determine eligibility for therapy on this study will be done only after obtaining informed consent. Assessments performed for clinical indications (not exclusively to determine study eligibility) may be used for baseline values even if the studies were done before informed consent was obtained.

All screening procedures must be performed within 30 days prior to day of initiating therapy unless otherwise stated. Screening and C1D1 procedures may be done on the same day, so long as patient completes screening procedures and is eligible prior to dosing. Re-screening of patients will be allowed, if all entry criteria are met during the re-screening phase time period (-30 days to -1 day). The screening procedures include:

9.1.1.1 Informed Consent

Screening assessments to confirm eligibility will be performed as per the schedule of assessments. Documented Informed consent must be obtained before any study specific procedure will be performed. We recognize that some patients travel from great distances to receive their care at Stanford. Therefore patients who have met with investigators and had an opportunity to hear about the trial and have had their questions answered, may submit a signed consent form from home at a later date via a high fidelity electronic means such as facsimile, computer scan, or smartphone camera image of the relevant signed pages of the consent form, as long as those images contain all relevant data on the signature page of the consent form, including dated signature of the subject and version date of the consent, and are legible. The Investigator may sign the consent form at a date different from the subject, but not prior to the subject signature date.

9.1.1.2 Medical history

Complete medical and surgical history, history of infections

9.1.1.3 Demographics

Data to be collected on patient characteristics at screening include:

-Demography (including: date of birth, age, patient initials, gender, childbearing potential, race and ethnicity, or as allowed by local regulations)

-ATC diagnosis and extent of disease, including:

 Date of diagnosis (collection date of the first path report confirming ATC/UTC)

 Site of active disease

 Prior antineoplastic therapies (medications, radiation, surgeries)

 Prior and Concomitant Medications, surgical and medical procedures

9.1.1.4 Review subject eligibility criteria

9.1.1.5 Review previous and concomitant medications

All other medications taken within 28 days before the first dose of treatment is administered will be noted in the clinical trial medication record and any changes to medications will be updated at the appropriate study visit.

9.1.1.6 Physical exam including vital signs, height and weight

Vital signs (temperature, pulse, respirations, blood pressure), height, weight

9.1.1.7 Performance status

Performance status evaluated prior to study entry

9.1.1.8 Adverse event assessment

Baseline adverse events will be assessed. See Section 7.4 for Adverse Event monitoring and reporting.

9.1.1.9 Hematology

Hgb, platelets, white blood cells (WBC), red blood cells (RBC), differential (basophils, eosinophils, lymphocytes, monocytes, neutrophils (% or absolute))

9.1.1.10 Serum chemistries

Albumin, ALT, AST, calcium, creatinine, total bilirubin, blood urea nitrogen (BUN) or urea, potassium, sodium, glucose. Creatinine clearance will be calculated using the serum creatinine value.

9.1.1.11 Pregnancy test (for females of child bearing potential)

At screening visit, serum pregnancy test will be performed. Following the screening assessment, urine pregnancy tests should be performed. Pregnancy test must be performed according to the date windows listed under schedule of assessments.

9.1.1.12 *Tumor assessment*

To be performed using radiographic imaging according to Section 9.1.4.1.

9.1.1.13 *Information to be collected on screening failures*

A patient who signs an informed consent but fails to satisfy all eligibility criteria for any reason will be considered a screen failure. The demographic information, informed consent, and documentation supporting the reason for screenfail will be completed for Screen Failure patients. No other data will be entered into the clinical database for patients who are screen failures, unless the patient experienced a Serious Adverse Event during the Screening Phase (see SAE Section 7.4 reporting details).

9.1.1.14 *Replacement policy*

If an eligible patient is unable to start therapy with study treatment, they may be replaced with another eligible patient if they have not received any study drug.

Apart from the above, patients will not be replaced on this study.

9.1.2 *Treatment period*

Following completion of screening procedures and verifying patient eligibility, the patient will be approved for treatment per protocol.

The study treatment phase begins on Cycle 1, Day 1 with the first administration of abemaciclib and will continue to receive treatment until disease progression by RECIST, unacceptable toxicity, withdrawal of consent, or discontinuation of the trial for any other reason whichever occurs first. Patients who have RECIST-defined PD as assessed by the investigator but who, in the opinion of the investigator, have evidence of continued clinical benefit from abemaciclib may continue to receive the study medication upon approval by the principal investigator. In such cases, these patients must continue to be followed for safety and efficacy assessments as per the schedule of assessments. Patients will be assessed as per visit schedule in Table 9-1.

9.1.3 *End of treatment visit including study completion and premature withdrawal*

Patients will be evaluated upon discontinuation of the study treatment by a clinic visit. At that time all assessments listed for End Of Treatment will be performed. A note will be entered into the clinical trial record will be completed, giving the date and reason for stopping the study treatment.

At a minimum, all patients who discontinue study treatment, including those who refuse to return for a final visit, will be contacted for safety evaluations during the 30 days following the last dose of treatment.

9.1.3.1 Criteria for patient withdrawal

Refer to Section 4.2 for details.

9.1.4 Assessment types

9.1.4.1 Efficacy assessments

Efficacy evaluations will be via revised RECIST 1.1 criteria on imaging performed at the conclusion of every 2 cycles. Target lesions will be identified prior to initiation of therapy on imaging and will be followed on subsequent imaging.

Physical exam findings of progressive disease will be considered as sufficient for documented progression if the record records biopsy proven tumor measurements in 2 dimensions and shows an increase in both dimensions of 20%.

Imaging exams will be according to standard of care guidelines to areas of known/suspected disease. These will include CT of the neck, chest, abdomen and pelvis as well as MRI of the brain. Other tests may be clinically indicated, these will be ordered according to disease and patient specific guidelines. Imaging of the brain will be required at baseline by CT or MRI per standard of care for Anaplastic Thyroid Cancer.

